## Adverse Events for the TAF Phase 3 Safety Population (Week 48)

### Summary of Adverse Events

Table 1-6 presents an overall summary of AEs by treatment group for the TAF Phase 3 Safety Population. Similar percentages of subjects in each treatment group had experienced at least 1 AE (TAF 70.2 %, 608 subjects; TDF 67.4%, 291 subjects) and had experienced at least 1 Grade 3 or 4 AE (TAF 4.5 %, 39 subjects; TDF 3.9 %, 17 subjects). In addition, 57 subjects (TAF 4.2%, 36 subjects; TDF 4.9 %, 21 subjects) had at least 1 SAE, with no subjects experiencing a treatment-related SAE. A similar percentage of subjects in each treatment group experienced an AE leading to discontinuation of study drugs (TAF 1.0%, 9 subjects; TDF 1.2%, 5 subjects). No deaths occurred in any subject on treatment. There were 2 deaths which occurred after treatment was discontinued and were considered non-treatment emergent (1 subject in each treatment group).

**Table 1-6. GS-US-320-0108 and GS-US-320-0110: Overall Summary of Adverse Events in the TAF Phase 3 Safety Population (Safety Analysis Set)**

Adverse Events	TAF 25 mg (N = 866)	TDF 300 mg (N = 432)
Subjects Experiencing Any AE	608 (70.2%)	291 (67.4%)
Subjects Experiencing Any Grade 2, 3, or 4 AE	221 (25.5%)	120 (27.8%)
Subjects Experiencing Any Grade 3 or 4 AE	39 (4.5%)	17 (3.9%)
Subjects Experiencing Any Study Drug-Related AE	123 (14.2%)	68 (15.7%)
Subjects Experiencing Any Grade 2, 3, or 4 Study Drug-Related AE	33 (3.8%)	21 (4.9%)
Subjects Experiencing Any Grade 3 or 4 Study Drug-Related AE	6 (0.7%)	2 (0.5%)
Subjects Experiencing Any SAE	36 (4.2%)	21 (4.9%)
Subjects Experiencing Any Study Drug-Related SAE	0	0
Subjects Experiencing Any AE Leading to Premature Study Drug Discontinuation	9 (1.0%)	5 (1.2%)
Subjects Experiencing Any AE Leading to Dose Modification or Study Drug Interruption	17 (2.0%)	7 (1.6%)
Death a	0	0

a Treatment-emergent death refers to the death occurred between the first dose date and the last dose date (inclusive). Adverse events were mapped according to MedDRA Version 18.

Treatment-emergent AEs was defined as follows:

- 1) Any AEs with onset date of on or after the study drug start date and no later than the study drug stop date for those who discontinued study drug permanently, or
- 2) Any AE with an onset date on or after the study drugs start date for those who had not discontinued study drug permanently, or
- 3) Any AEs leading to study drug discontinuation

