#### **Adverse Events**

Following initiation of study medication, collect all AEs, regardless of cause or relationship, until 30 days after last administration of study IMP. AEs must be reported to the CRF/eCRF database as instructed.

All AEs should be followed up until resolution or until the adverse event is stable, if possible. Gilead Sciences may request that certain AEs be followed beyond the protocol defined follow up period.

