#### **Serious Adverse Events**

All SAEs, regardless of cause or relationship, that occurs after the subject first consents to participate in the study (i.e., signing the informed consent) and throughout the duration of the study, including the protocol–required post treatment follow-up period, must be reported to the CRF/eCRF database and Gilead Pharmacovigilance and Epidemiology (PVE), previously known as Drug Safety and Public Health, as instructed. This also includes any SAEs resulting from protocol-associated procedures performed after informed consent is signed.

Any SAEs and deaths that occur after the post treatment follow-up visit but within 30 days of the last dose of study IMP, regardless of causality, should also be reported.

Investigators are not obligated to actively seek SAEs after the protocol defined follow up 30 days period; however, if the investigator learns of any SAEs that occur after study participation has concluded and the event is deemed relevant to the use of IMP, he/she should promptly document and report the event to Gilead PVE.

- All AEs and SAEs will be recorded in the CRF/eCRF database within the timelines outlined in the CRF/eCRF completion guideline.

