#### 7.5.5.1. For subjects on TDF:

- For subjects with baseline eGFRCKD-EPI  $\geq 50$  mL/min/1.73m^2 that decline to  $< 50$  mL/min/1.73m^2 at any post-baseline visit:
  - If the eGFRCKD-EPI is confirmed to be  $\geq 30$  mL/min/1.73m^2 and  $< 50$  mL/min/1.73m^2, the subject will be required to undergo dose modification to every other day dosing of TDF
  - If the eGFRCKD-EPI is confirmed to be  $\geq 30$  mL/min/1.73m^2 and  $< 50$  mL/min/1.73m^2, and the subject has undergone dose modification to every other day dosing of TDF and subsequently develops a confirmed eGFRCKD-EPI  $\geq 50$  mL/min/1.73m^2, the subject may revert to once daily dosing of TDF after discussion with the Gilead Medical Monitor
- For all subjects with a post-baseline eGFRCKD-EPI  $< 30$  mL/min/1.73 m^2 and  $\geq 15$  mL/min/1.73 m^2:
  - If the eGFRCKD-EPI is confirmed to be  $< 30$  mL/min/1.73m^2 and  $\geq 15$  mL/min/1.73 m^2, the subject will be required to undergo dose modification to every 96 hours dosing of TDF
  - If the eGFRCKD-EPI is confirmed to be  $< 30$  mL/min/1.73 m^2 and  $\geq 15$  mL/min/1.73 m^2, and the subject has undergone dose modification to once every 96 hours dosing of TDF and subsequently develops a confirmed CLCr  $\geq 30$  mL/min/1.73 m^2, the subject may revert to every other day dosing of study drug after discussion with the Gilead Medical Monitor
- For all subjects with a post-baseline eGFRCKD-EPI  $< 15$  mL/min/1.73 m^2:
  - If the eGFRCKD-EPI is confirmed to be  $< 15$  mL/min/1.73 m^2, the subject will be required to permanently discontinue treatment according to Section 7.5.5.3

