7.1.6. Treatment-Emergent Adverse Events

7.1.6.1. Definition of Treatment-Emergent Adverse Events

Summaries of treatment-emergent AEs will be provided for randomized CCI [REDACTED]

Treatment-emergent AEs occurring during the randomized phase are defined as:

- Any AE with onset date on or after the randomized study drug start date and no later than the minimum of the randomized study drug stop date + 3 days CCI [REDACTED], for those who discontinued randomized study drug permanently, or
- Any AE with onset date on or after the randomized study drug start date for those who are still on the randomized study drug, or
- Any AE leading to randomized study drug discontinuation.

CCI [REDACTED]

- [REDACTED]
- [REDACTED]
- [REDACTED]

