7.1.7. Summaries of Adverse Events and Deaths

A brief summary of AEs (ie, the number and percentage of subjects) will be presented by treatment group for the following: (1) any treatment-emergent AE, (2) any Grade 3 or 4 treatment-emergent AE, (3) any Grade 2, 3 or 4 treatment-emergent AE, (4) any treatment-emergent study drug-related AE, (5) any Grade 3 or 4 treatment-emergent study drug-related AE, (6) any Grade 2, 3 or 4 treatment-emergent study drug-related AE, (7) any treatment-emergent SAE, (8) any treatment-emergent study drug-related SAE, (9) any treatment-emergent AE leading to premature study drug discontinuation, (10) any treatment-emergent AE leading to dose modification or study drug interruption, and (11) any treatment-emergent death.

Treatment-emergent death during the randomized phase refers to death that occurs between the first dose date of the randomized study drug and the minimum of the last dose date of the randomized study drug + 3 days CCI [REDACTED] for those who discontinued randomized study drug permanently. CCI [REDACTED]

Summaries (number and percentage of subjects) of AEs (by SOC, HLT [if specified below], and PT) will be provided by treatment group and overall using the Safety Analysis Set for the randomized phase CCI [REDACTED] as follows:

- All treatment-emergent AEs summarized by SOC, HLT, and PT
- Any Grade 3 or 4 treatment-emergent AEs
- Any Grade 2, 3, or 4 treatment-emergent AEs
- All treatment-emergent study drug-related AE summarized by SOC, HLT, and PT
- Any Grade 3 or 4 treatment-emergent study drug-related AEs
- Any Grade 2, 3, or 4 treatment-emergent study drug-related AEs
- All treatment-emergent SAEs

- All treatment-emergent study drug-related SAEs
- All treatment-emergent AEs leading to premature discontinuation from study drug
- All treatment-emergent AEs leading to dose modification or study drug interruption

Multiple events will be counted once only per subject in each summary. For data presentation, SOC (and HLT) will be ordered alphabetically, with PT sorted by decreasing total frequency. For summaries by severity grade, the most severe event will be selected.

In addition to the by-treatment summaries, data listings will be provided for the following:

- All AEs
- Grade 3 and 4 AEs
- SAEs
- Study drug-related SAEs
- Deaths
- AEs leading to premature discontinuation of study drug
- AEs leading to dose modification or study drug interruption

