7.9. Changes From Protocol-Specified Safety Analyses

Treatment-emergent AE and lab abnormality in randomized phase was defined as any AE or lab abnormality that begins on or after the first dose date of study drug up to the last dose date in the protocol, and is updated in this SAP. Treatment-emergent AE occurring in the randomized phase is defined as any AE with onset date on or after the first dose date of the randomized study and no later than the minimum of the randomized study drug stop date + 3 days CCI [REDACTED], if applicable for the randomized phase. Treatment-emergent laboratory abnormalities occurring in the randomized phase are defined as values that increase by at least 1 toxicity grade from baseline at any postbaseline visit up to and including the minimum of the randomized study drug stop date + 3 days CCI [REDACTED] for the randomized phase. This change was made as labs performed 1-2 days after study drug stopped were being excluded causing the measurement for the timepoint to be missed, even though protocol specified visit windows allowed for labs to be performed in a short period after the study drug was stopped.

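### By-arm AE, SAE and death tables end 3 days after the last randomized dose, although these events are collected to at least 30 days; a 30-day table by arm should be added

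*SAP*

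**What the plan says.** For subjects who stopped randomized drug permanently, SAP 7.1.6.1 treats an AE as treatment-emergent if its onset is "no later than the minimum of the randomized study drug stop date + 3 days". The second term of that minimum is redacted, but it can only shorten the window. There is one exception without a date limit: "Any AE leading to randomized study drug discontinuation". SAP 7.1.7 limits treatment-emergent deaths in the same way, to "the minimum of the last dose date of the randomized study drug + 3 days". The by-arm AE, SAE and death summaries all rest on these definitions. By-subject listings of all AEs, SAEs and deaths are also planned, and SAP Section 3 says listings use the randomized treatment group.

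Collection runs longer. Protocol 7.3 tells sites to "collect all AEs, regardless of cause or relationship, until 30 days after last administration of study IMP". SAEs are to be reported "throughout the duration of the study, including the protocol–required post treatment follow-up period", and SAEs and deaths within 30 days of the last dose are reportable even if follow-up visits have ended.

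The protocol's own analysis window is the narrowest of the three. Sections 8.6 and 8.6.4 end by-group safety summaries and treatment-emergent AEs at the last dose. SAP 7.9 records the extension by 3 days and gives its reason: "This change was made as labs performed 1-2 days after study drug stopped were being excluded".

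**The concern.** The 3 days were chosen so that end-of-treatment laboratory samples would not be lost. Neither document says why the same interval suits AEs, SAEs or deaths. The SAP already varies its windows by type of data: Section 3.7.2 allows 3 days after the last dose for laboratory tests and 14 days for DXA.

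The protocol also expects harm after stopping. Section 7.5.6.2 sets out management of hepatitis exacerbation in subjects who have discontinued study medication, and Section 7.5.6.1 warns that stopping could lead to decompensation in those with bridging fibrosis or cirrhosis. A new event of this kind on days 4 to 30 is collected but not tabulated by arm. A subject whose SAE begins on drug and is fatal on day 4 or later appears in the SAE table but not in the death count.

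What is at stake is the by-arm count of deaths and SAEs among subjects who stop early. They are not a random subset: for example, confirmed eGFR below 15 mL/min/1.73 m² requires permanent discontinuation (Protocol 6.6 and 7.5.5.3).

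**Working it through.** The plan states no figure to reproduce here, and no power or error rate is involved. The check compares the windows and then sizes the gap.

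**1. Windows after the last dose (date D)**

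| Rule | Source | Last day covered |
|---|---|---|
| AE collection | Protocol 7.3 | D+30 |
| SAE and death reporting | Protocol 7.3 | at least D+30 |
| Protocol analysis | Protocol 8.6, 8.6.4 | D |
| SAP by-arm tables | SAP 7.1.6.1, 7.1.7 | D+3 |

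Share of the 30 post-dose collection days outside the SAP tables: (30 − 3)/30 = 27/30 = 90%. Under the protocol's rule it would be 30/30 = 100%. These are shares of days, not of events.

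**2. What falls outside the by-arm tables**

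- A new AE or SAE with onset on D+4 to D+30: not tabulated.
- An AE that led to discontinuation: tabulated, whatever its onset.
- An SAE starting by D+3 and fatal on D+4 or later: tabulated as an SAE, not as a death.
- Any other death on D+4 or later: not tabulated.

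**3. Weight of one subject**

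With about 25 per arm (SAP 1.2): 1/25 = 4 percentage points.

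**4. How many SAEs might be affected (illustration only)**

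Base rate from the pooled Phase 3 data in Protocol 1.2.3: 36 + 21 = 57 subjects with an SAE; mean exposure 58.9 weeks in 866 TAF subjects and 59.0 weeks in 432 TDF subjects.

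Rate = 57 / (866 × 58.9 + 432 × 59.0) = 57 / 76,495.4 = 0.000745 per person-week.

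Expected SAE subjects in days 4 to 30 = rate × number stopping × 27/7 weeks. P(at least one) = 1 − exp(−expected).

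| Subjects stopping without study TAF (assumed) | Expected, Phase 3 rate | Expected, 20 times that rate (assumed) | P(at least one), 20 times |
|---|---|---|---|
| 2 | 0.006 | 0.115 | 0.11 |
| 5 | 0.014 | 0.287 | 0.25 |
| 10 | 0.029 | 0.575 | 0.44 |

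For scale, the Phase 3 discontinuation share of 63/1298 = 4.9% would give about 2.4 of 50 subjects. The 20-fold multiplier is an assumption to bracket a sicker population just after stopping; the documents give no such rate.

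**The case against.** The strongest reply is that collecting events longer than the treatment-emergent window is ordinary, that the protocol set an even shorter window, and that nothing is hidden. Most of this stands. The SAP widened the protocol's window and recorded the change. The events remain in listings by randomized arm, and with about 50 subjects a reader can count them by hand. The discontinuation exception also covers much of the obvious scenario, a subject taken off drug because of a serious event. All safety results are descriptive, so no test is affected.

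It does not answer why a laboratory-timing interval should govern deaths and SAEs, or why the reader must build the by-arm count from listings. Nor would an added table conflict with the protocol, since Section 8.2.1.2 allows treatment-free follow-up data to be summarized or listed separately.

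Four stronger readings are tempting but unsupported:

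- *The SAP cut back what the protocol planned.* It did the reverse, from D to D+3.
- *The window disadvantages Arm B.* At low eGFR, "the subject will be required to undergo dose modification to every 96 hours dosing of TDF", which seems longer than 3 days. But D to D+3 already covers four calendar dates. Only the part of D+4 before the next dose would have been due is outside, and the date rule is identical in both arms.
- *The Phase 3 deaths show the size of the loss.* The protocol reports that "There were 2 deaths which occurred after treatment was discontinued and were considered non-treatment emergent", one per group, while the table shows none. That rule ended at the last dose, and the timing of the deaths is not given. Nothing shows that 3 days would have missed them or that 30 days would have caught them.
- *One or two such events could reverse the safety picture.* The primary safety endpoint is change in eGFR, and the expected number of untabulated events is small.

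**Conclusion.** The point holds as a specific, low-cost improvement to the tables. By-arm summaries omit new AEs and SAEs with onset on days 4 to 30 and every death from day 4, although the protocol requires these data to at least day 30 and anticipates post-treatment exacerbation. The gap begins in the protocol's own analysis window, and the SAP closes 3 of its 30 days.

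The likely count is low: 0.006 to 0.029 SAE subjects at the Phase 3 rate for 2 to 10 subjects stopping, and more only under much higher assumed rates. Each subject added would move an arm's percentage by about 4 points.

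This rests on three assumptions: arms of about 25; no by-arm post-treatment table in the redacted text (none is visible); and relevance mainly to subjects who stop without going on to study TAF. How later events are tabulated for those who continue is redacted.

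**What to change.** In SAP 7.1.7, for subjects who stop randomized drug without continuing on study TAF, add by-arm summaries of deaths, SAEs and AEs to last dose + 30 days, using the same window in both arms. Present them beside the +3-day tables. For subjects who continue on study TAF, keep the cut at its start. Record the addition in SAP 7.9.

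Do not extend the by-arm death count to the whole study. Protocol 6.4.1 specifies the 24-week treatment-free follow-up only for subjects who received TAF, so later deaths could be found more completely in one arm. List deaths after day 30, with a note on that difference.

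The cost is one date flag and repeats of existing tables on data already collected. The downside is that some added events will occur after other HBV therapy has started, and possibly more than a few, because Protocol 1.3 says these patients need lifelong antiviral treatment. A footnote should identify those events.

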7.2. Laboratory Evaluations

Laboratory data collected during the study will be analyzed and summarized using both quantitative and qualitative methods. Summaries of laboratory data will be provided for the entire study period based on Safety Analysis. Analysis will be based on values reported in conventional units. No formal statistical testing is planned.

7.2.1. Summaries of Numeric Laboratory Results

Descriptive statistics (sample size, mean, SD, median, Q1, Q3, minimum, and maximum) will be provided by treatment group for each laboratory test during the entire study period specified in the study protocol as follows:

- Baseline values
- Values at each postbaseline analysis window
- Change from baseline to each postbaseline analysis window
- Percentage change from baseline to each postbaseline analysis window (if specified)

7.2.1.1. Metabolic Assessments

For the lipid panel and glucose measurements, only those under fasting status will be summarized.

Fasting lipid data (including total cholesterol, LDL, HDL and triglycerides) will also be analyzed using the following Adult Treatment Panel (ATP) III categories {[National Cholesterol Education Program \(NCEP\) 2001](#)}:

- **For total cholesterol (mg/dL):** < 200 (desirable), 200-239 (borderline high), and ≥ 240 (high)
- **For LDL (mg/dL):** < 100 (optimal), 100-129 (near optimal/above optimal), 130-159 (borderline high), 160-189 (high), and ≥ 190 (very high)
- **For HDL (mg/dL):** < 40 (low), 40-59 (normal), and ≥ 60 (high)
- **For triglycerides (mg/dL):** < 150 (normal), 150-199 (borderline high), 200-499 (high), and ≥ 500 (very high)

The number and proportion of subjects for the above categories of each lipid parameter will be summarized by its baseline category for each treatment group at each visit.

7.2.1.2. Calcium Correlated for Albumin

Calcium corrected for albumin will be calculated and summarized. The following formula will be used when both serum calcium and albumin results for a given blood draw are available and serum albumin value is < 4.0 g/dL.

Calcium corrected for albumin (mg/dL) = serum calcium (mg/dL) + $0.8 \times (4.0 - \text{albumin (g/dL)})$.

When albumin value is ≥ 4.0 g/dL, the actual calcium results will be used. Toxicity grading for calcium will be applied based on the corrected values.

7.2.2. Graded Laboratory Values

The criteria specified in the protocol will be used to grade laboratory results as Grade 0, Grade 1 (mild), Grade 2 (moderate), Grade 3 (severe) or Grade 4 (life-threatening). Grade 0 includes all values that do not meet criteria for an abnormality of at least Grade 1. Some laboratory tests have criteria for both increased and decreased levels; analysis for each direction (ie, increased, decreased) will be presented separately.

For triglycerides, LDL, and total cholesterol, the protocol-specified toxicity grade scale is for fasting test values; non-fasting lipid results (or lipid results without known fasting status) will not be graded or summarized by toxicity grades.

If any laboratory toxicity grading scale overlaps with normal reference ranges (eg, Grade 1 scale overlaps with normal reference ranges), laboratory values within normal range will not be graded except for lipid tests.

7.2.2.1. Treatment-Emergent Laboratory Abnormalities

Treatment-emergent laboratory abnormalities occurring in the randomized phase are defined as values that increase by at least 1 toxicity grade from baseline at any postbaseline visit up to and including the minimum of the randomized study drug stop date + 3 days **CCI** [REDACTED], for those who discontinued randomized study drug prematurely, or values that increase by at least 1 toxicity grade from baseline at any postbaseline visit for those who are still on the randomized study drug. If the relevant baseline laboratory data are missing, any laboratory abnormality of at least Grade 1 will be considered treatment-emergent.

CCI [REDACTED]

Fasting glucose and nonfasting glucose are graded based on different grading scales. Treatment-emergent laboratory abnormalities will be summarized for fasting glucose and nonfasting glucose separately.

7.2.2.2. Treatment-Emergent Marked Laboratory Abnormalities

Treatment-emergent marked laboratory abnormalities occurring in the randomized phase are defined as values that worsen by at least 3 grades from baseline at any postbaseline visit up to and including the minimum of the randomized study drug stop date + 3 days **CCI** [REDACTED], for those who discontinued randomized study drug prematurely, or values that worsen by at least 3 grades from baseline at any postbaseline visit for those who are still on randomized study drug. If relevant baseline laboratory data are missing, any laboratory abnormalities of at least Grade 3 or 4 will be considered as treatment-emergent marked laboratory abnormalities.

CCI [REDACTED]

7.2.2.3. Summaries of Laboratory Abnormalities

Laboratory data that are categorical will be summarized using the number and percentage of subjects in the study with the given response at baseline and each scheduled postbaseline visit.

The following summaries (number and percentage of subjects) of laboratory abnormalities will be provided by treatment group (subjects categorized according to most severe abnormality grade) for the randomized phase CCI :

- Treatment-emergent laboratory abnormalities
- Treatment-emergent Grade 3 and 4 laboratory abnormalities
- Treatment-emergent marked laboratory abnormalities

For all summaries of laboratory abnormalities, the denominator is the number of subjects with any non-missing postbaseline value in the given study period. A listing of treatment-emergent Grade 3 or 4 laboratory abnormalities will be provided.

